Project Title: Pharmacodynamic Effects of Different Ticagrelor Maintenance Dosing Regimens With and Without Aspirin in Patients with Diabetes Mellitus: The OPTIMUS (Optimizing Antiplatelet Therapy in Diabetes Mellitus)-7 Study

- Investigators: [name], PhD, [name], [name], J. [name], [name], AAS
- **2.** Abstract: Dual antiplatelet therapy (DAPT) with aspirin and a  $P2Y_{12}$  inhibitor is the standard of care for the prevention of thrombotic complications in patients with coronary artery disease (CAD) undergoing percutaneous coronary interventions (PCI). However, such ischemic benefit occurs at the expense of enhanced bleeding, the risk of which increases in a graded fashion with prolonged exposure to DAPT. Recent studies have shown that withdrawing aspirin and maintaining P2Y12 inhibitor monotherapy for up to 12 months post-PCI, after a brief period of DAPT, reduces bleeding without increasing ischemic harm. Such effects have shown to of particular benefit in patients with diabetes mellitus (DM). However, if an aspirin-free approach can be considered after this time frame is a matter of debate. In fact, current guidelines recommend maintaining P2Y12 inhibiting therapy for high risk patients but which all imply background use of aspirin. P2Y12 inhibitors for long-term (beyond 12 months) secondary prevention mainly include clopidogrel and ticagrelor. In particular, the dosing regimen for clopidogrel remains the standard 75 mg qd, whereas ticagrelor dosing is recommended to be reduced from 90 mg bid to 60 mg bid. However, of these regimens the pharmacodynamics (PD) effects of ticagrelor 60 mg in the absence of aspirin has not yet been tested. Because DM patients are likely to continue with long-term

P2Y12 inhibitor therapy, defining the optimal antithrombotic approach for these patients is of critical importance. In light of the above made observations, patients with DM represent an ideal population to define the antiplatelet effects of a ticagrelor 60 mg monotherapy regimen. The aim of this study is to assess the PD effects of ticagrelor 60 mg with and without aspirin therapy in CAD patients and to compare this with a standard DAPT regimen of aspirin plus clopidogrel. Data will be collected and then entered into a secure database. For the scope of this study, the REDCap system will be used to store study related data, and all patients will be identified using a subject identifier. Telephone numbers, street addresses and email addresses may be used to contact the patient, however this information will not be stored in REDCap.

## 3. Background and Significance:

Dual antiplatelet therapy (DAPT) with aspirin and a P2Y12 inhibitor is the standard of care for the prevention of thrombotic complications in patients with coronary artery disease (CAD) undergoing percutaneous coronary interventions (PCI) [1]. However, such ischemic benefit occurs at the expense of enhanced bleeding, the risk of which increases in a graded fashion with prolonged exposure to DAPT [1,2]. In light of the adverse prognosis associated with bleeding, there has been much attention toward identifying antithrombotic regimens that can reduce the risk of bleeding while maintaining efficacy post-PCI [3,4]. Among these, maintaining P2Y12 inhibitor monotherapy, after a brief period of DAPT, has emerged as a promising bleeding reduction strategy in a number of investigations [5]. Such aspirin-free approach has been postulated based on pharmacodynamic investigations demonstrating that, on background of potent P2Y12 inhibiting therapy, including ticagrelor, aspirin offers limited antiplatelet effect and may therefore mainly contribute to bleeding potential [5]. Recently, the Ticagrelor With Aspirin or Alone in High-Risk Patients after Coronary Intervention (TWILIGHT) trial showed that among high-risk PCI patients, after 3 months of DAPT, P2Y12 inhibitor monotherapy with ticagrelor 90 mg bid (without aspirin) reduced bleeding without increasing ischemic harm after 12 months of therapy compared with ticagrelor 90 mg bid used in adjunct to aspirin [6].

Although the TWILIGHT trial provides important insights on the benefits of an aspirin-free approach within the first year after undergoing PCI, it does not address how to manage patients after this time frame. Current guidelines recommend maintaining P2Y12 inhibiting therapy for high risk patients but which all imply background use of aspirin [1].  $P2Y_{12}$ inhibitors for long-term (beyond 12 months) secondary prevention mainly include clopidogrel and ticagrelor [1]. In particular, the dosing regimen for clopidogrel remains the standard 75 mg qd, whereas ticagrelor dosing is recommended to be reduced from 90 mg bid to 60 mg bid [1]. In light of the improved outcomes associated with a ticagrelor 90 mg bid regimen without aspirin during the first year after PCI demonstrated in the TWILIGHT trial, understanding the differential effects of different antiplatelet combinations, in particular the effects of long-term ticagrelor at a 60 mg bid regimen without aspirin, is of utmost clinical interest. Importantly, pharmacodynamic (PD) studies have shown that the 90 and 60 mg ticagrelor regimens provide similar platelet inhibitory effects [7-9]. However, the 60 mg regimen has been associated with an overall more favorable safety profile which is the rationale for it being recommended for long-term secondary prevention in patients with CAD, irrespective of whether they underwent PCI [10]. However, the PD effects of ticagrelor 60 mg in the absence of aspirin have not yet been tested.

Patients with diabetes mellitus (DM) are known to be at high-risk for both ischemic and bleeding complications post-PCI [11,12]. A number of factors which commonly affect patients with DM contribute to these observations, including the complexity of coronary interventions, endothelial dysfunction, concomitant comorbidities, and dysregulation of hemostatic and thrombotic processes [11,12]. Importantly, the prevalence of DM (mostly type 2) in the past decade has increased by 30% globally, an observation also reflected in PCI trials wherein DM is a more frequently encountered risk factor, and is projected to markedly increase in the upcoming decades [13]. These observations highlight the importance of defining optimal post-PCI pharmacotherapy in patients with DM. Of note, a pre-defined subgroup analysis of the TWILIGHT trial showed that among patients with DM patients undergoing PCI, ticagrelor monotherapy significantly reduced clinically relevant bleeding compared with ticagrelor plus aspirin, without increasing the risk of ischemic events [14]. In particular, the reduction in net adverse cardiac events in DM patients treated with a ticagrelor monotherapy strategy was markedly greater than that observed in non-DM patients [14]. While the potent level of P2Y12 blockade achieved with ticagrelor limits the adjunctive benefits associated with aspirin therapy, the synergism on platelet inhibitory effects with the use aspirin in the presence of more modest levels of P2Y12 blockade induced by clopidogrel may be more relevant particularly in patients with DM [15]. Because DM patients are likely to continue with more potent antithrombotic treatment regimens for long-term secondary prevention beyond 12 months [1,16], defining the optimal antithrombotic approach for these patients is of critical importance. In light of the above made observations, patients with DM represent an ideal population to define the antiplatelet effects of a ticagrelor 60 mg monotherapy regimen.

#### 4. Specific Aims:

The aim of this study is to assess the PD effects of ticagrelor 60 mg with and without aspirin therapy in CAD patients and to compare this with a standard DAPT regimen of aspirin plus clopidogrel. We hypothesize that withdrawal of aspirin therapy among ticagrelor treated patients will not result in significant changes in ADP-induced platelet reactivity and will provide more effective platelet inhibition compared with aspirin plus clopidogrel. The results of the study will allow defining the best antiplatelet strategy when transitioning patients to long-term antiplatelet treatment.

[figure not shown]
# 5. Research Plan:

#### **Research Design**

This will be a prospective, randomized, open-label study conducted in patients with CAD and diagnosis of DM. Patients can be on any background antiplatelet therapy, including aspirin or any P2Y12 inhibitor (clopidogrel, ticagrelor or prasugrel). The study will be performed at the Division of Cardiology of University of Florida Health, Jacksonville, Florida and patients will be recruited within the Cardiovascular services of our Institution. Patients will be screened by Cardiology Research staff, who will verify that all candidates meet inclusion and exclusion criteria. Results from blood tests performed within the last 90 days will be considered valid for screening purposes. If these are not available, a blood sample will be collected for the screening phase after the patient has signed informed consent.

Eligible patients will enter a 7-10 day run-in phase with aspirin 81 mg/ qd plus ticagrelor 90 mg bid after which they will discontinue aspirin and maintain ticagrelor 90 mg bid monotherapy for  $10\pm 3$  days. After this period, patients will be randomized using a randomly generated computer sequence in a 1:1:1 fashion to one of three treatment groups: a) ticagrelor 60 mg bid monotherapy; b) aspirin 81 mg qd plus ticagrelor 60 mg bid; c) aspirin 81 mg qd plus clopidogrel 75 mg qd. Randomized treatment will be maintained for  $10\pm 3$  days. The approach of having a run-in phase with aspirin plus ticagrelor 90 mg followed by ticagrelor 90 mg monotherapy is in line with the TWILIGHT trial to assess for tolerability and compliance with ticagrelor therapy [6, 17]. The approach of having an aspirin plus ticagrelor 60 mg regimen as well as an aspirin plus clopidogrel regimen is reflective of guideline recommendations for long-term secondary prevention [1,16]. The current investigation will test the hypothesis that the experimental strategy of ticagrelor 60 mg monotherapy will not result in significant changes in P2Y12 inhibitory effects compared with aspirin plus ticagrelor 60 mg and will provide more effective platelet inhibition compared with aspirin plus clopidogrel. The study design is illustrated in Figure 1 and a further breakdown of what will occur during the course of the study:

## Figure 1. OPTIMUS-7 study design.

- Potential subjects will first be screened by research personnel to see if they are eligible for the study. Results from blood tests performed within the last 90 days which they would have performed as part of their standard of care will be considered valid for screening purposes.
- If the potential subject is a woman of childbearing potential, a pregnancy test will be done. If subject is found to be pregnant, the participation in this study will end.
- If subject is eligible for the study based on the screening results, the subject will start the study procedures as outlined below:
  - Every participant will start a so called run-in phase during and will be treated with aspirin 81mg once a day, and Ticagrelor 90mg twice a day for 7-10 days. After that, the participant will stop taking the aspirin and only take the Ticagrelor 90mg for 10±3 days. This run-in phase is to make sure that subjects are able to take the medication without side effects.

- After completing the run-in part of the study, subjects will be randomized to one of three medication groups and take study medication for 10 ± 3 days:
  - a) Ticagrelor 60mg twice daily (without aspirin)
  - b) Ticagrelor 60mg twice daily, plus aspirin 81mg once daily
  - c) Clopidogrel 75mg once daily, plus aspirin 81mg once daily

Blood sampling for PD testing will be performed at 4 time points: a) after completing 1week aspirin plus ticagrelor 90 mg run-in phase; b) after completing  $10\pm3$  days of treatment with ticagrelor 90 mg monotherapy; c) after completing  $10\pm3$  days of randomized treatment. At each time point PD assessments will be performed  $12 \pm 2$  hours after last ticagrelor dose and 24 hours after last clopidogrel dose in order to define trough levels of platelet inhibition. At the last time point (after  $10\pm3$  days of randomized treatment) blood samples will also be collected 2 hours after administration of the antiplatelet regimen in order to assess for peak levels of platelet inhibition. The Ticagrelor (Brilinta) tablets are being provided by AstraZeneca. The Clopidogrel and aspirin will be provided by the Cardiovascular Research Department. All medications will dispensed by the Cardiovascular Research Department and will be packaged using supplies and guidelines provided by UF Health Research Pharmacy.

## **Study Population**

#### Inclusion criteria:

For inclusion in the study patients should fulfill the following criteria:

- 1. Provision of informed consent prior to any study specific procedures
- 2. Men or women  $\geq 18$  years of age

3. Diagnosed with type 2 DM defined by ongoing glucose lowering therapy (oral medications and/or insulin) treatment for at least 1 month

Known angiographically defined CAD (including a history of previous PCI, CABG, or >50% stenosis in a major epicardial vessel) on standard of care antiplatelet therapy\*
\*Patients can be treated with any background antiplatelet treatment regimen as part of their standard of care, including aspirin and/or any P2Y12 inhibitor (clopidogrel, ticagrelor, prasugrel).

#### *Exclusion criteria:*

- 1. PCI < 6 months prior
- 2. Recent (< 6 months) type I myocardial infarction
- Anticipated concomitant oral or intravenous therapy with strong cytochrome P450 3A4 (CYP3A4) inhibitors or CYP3A4 substrates with narrow therapeutic indices that cannot be stopped for the course of the study:
  - Strong inhibitors: ketoconazole, itraconazole, voriconazole, telithromycin,
     clarithromycin (but not erythromycin or azithromycin), nefazadone, ritonavir,
     saquinavir, nelfinavir, indinavir, atanazavir
  - CYP3A4 substrates with narrow therapeutic index: quinidine, simvastatin at doses
     >40 mg daily or lovastatin at doses >40 mg daily
- Anticipated concomitant oral or intravenous therapry of strong CYP3A inducers (phenytoin, rifampin, phenobarb, carbamazepine)
- 5. Need for chronic oral anticoagulant therapy or chronic low-molecular-weight heparin (at venous thrombosis treatment not prophylaxis doses)
- 6. Patients with known bleeding diathesis or coagulation disorder

- History of previous intracerebral bleed at any time, gastrointestinal (GI) bleed within the past 6 months prior to randomization, or major surgery within 30 days prior to randomization
- 8. Active pathological bleeding
- 9. Hypersensitivity to aspirin, ticagrelor or clopidogrel
- 10. Increased risk of bradycardic events (eg, known sick sinus syndrome, second or third degree AV block or previous documented syncope suspected to be due to bradycardia) unless treated with a pacemaker
- 11. Known severe liver disease
- 12. Renal failure requiring dialysis
- 13. Known platelet count <80x10^6/mL
- 14. Known hemoglobin <9 g/dL
- 15. Pregnant or breastfeeding women.

\*Women of childbearing age must use reliable birth control (i.e. oral contraceptives) while participating in the study.

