#### 6. Possible Discomforts and Risk:

In clinical trials, the most important adverse effect associated with the use of ticagrelor was bleeding. The risk of major bleeding with ticagrelor 90 and 60 mg was 2.8% and 2.3%, respectively; the combined risk of intracranial hemorrhage or fatal bleeding was <1% [7,27]. However, such bleeding prevalence occurred in the setting of long-term trial (median follow-up of 9 and 33 months in PLATO and PEGASUS) with bleeding events that accrued over time, while our study is limited to only  $30 \pm 3$  days of therapy. Ticagrelor will be compared with clopidogrel, which is also associated with an increased risk of bleeding compared with placebo [28]. We do not anticipate that ticagrelor will significantly increase the risk of bleeding compared with clopidogrel. Dyspnea has been reported as the main non-bleeding side effect with ticagrelor and occurs in up to 15.8% of patients [7,27]. Below is a complete lists of potential medication risks:

- Bleeding
- Dyspnea (shortness of breath)
- Headache
- Cough
- Mild to moderate diarrhea
- Nausea
- Hypotension (low blood pressure)
- Hypertension
- Dizziness
- Non-cardiac chest pain
- Back Pain
- Fatigue
- Cardiac (heart) chest pain

Patients who discontinue ticagrelor therapy will be switched back to their standard of care treatment regimen.

All clinical events described above, if they were to occur, as well as death, myocardial infarction, stroke, and urgent revascularization procedure with PCI or coronary artery bypass grafting will be recorded. All serious adverse events will be submitted to the AstraZeneca Product Safety mailbox. Bleeding data will be collected using BARC definitions [24]. The study will have a DSMB, comprised of 2 faculty members (2 cardiologists), not directly involved in

the research. In the event of a report of a serious adverse event the local committee will meet and antiplatelet treatment management will be managed according to physician recommendation.

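### The 30-day surgery and 6-month GI-bleed exclusions count back from randomisation, but study aspirin plus ticagrelor 90 mg starts 14-23 days earlier

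*Combined protocol and SAP*

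**What the plan says.** The criterion, under Exclusion criteria in the Study Population part of Section 5, excludes "gastrointestinal (GI) bleed within the past 6 months prior to randomization, or major surgery within 30 days prior to randomization". Randomisation is the only reference date for either window. The intracerebral-bleed part of the same criterion applies at any time and is not affected.

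Research Design (Section 5) gives the order of events. Staff screen first, "who will verify that all candidates meet inclusion and exclusion criteria". Then "Eligible patients will enter a 7-10 day run-in phase with aspirin 81 mg/ qd plus ticagrelor 90 mg bid", followed by ticagrelor 90 mg twice daily alone for 10±3 days. Only then: "After this period, patients will be randomized using a randomly generated computer sequence in a 1:1:1 fashion". The text under Figure 1 confirms the order: "After completing the run-in part of the study, subjects will be randomized to one of three medication groups".

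On prior treatment, the inclusion criteria state: "Patients can be treated with any background antiplatelet treatment regimen as part of their standard of care". Section 6 states: "In clinical trials, the most important adverse effect associated with the use of ticagrelor was bleeding".

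**The concern.** An exclusion for recent surgery or recent GI bleeding protects a patient from the moment study drug adds to bleeding risk. Here that moment is the first run-in dose, not randomisation. A patient can meet the criterion at randomisation without having met it when aspirin plus ticagrelor 90 mg began.

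Three features of the protocol give this some weight:

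- The run-in combines aspirin with the 90 mg dose, whereas the background section describes the 60 mg dose as having the more favourable safety profile.
- Patients may enter on aspirin without a P2Y12 inhibitor. For them the run-in is a step up in antiplatelet therapy.
- Previous CABG is a route to inclusion, and the separate 6-month exclusions cover PCI and type I myocardial infarction but not CABG. For a CABG patient with neither of those, the 30-day surgery rule is the only post-operative interval stated.

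What is at stake is participant safety early in the run-in, not the validity of the platelet-reactivity comparison.

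**Working it through.** The plan states no interval from first dose to randomisation, so there is no figure to reproduce. It follows by date arithmetic.

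**Inputs**
- Run-in part 1 (aspirin plus ticagrelor 90 mg): 7-10 days (Research Design).
- Run-in part 2 (ticagrelor 90 mg alone): 10±3 days, that is 7-13 days (Research Design and Figure 1 text).
- Surgery window: 30 days before randomisation (Exclusion criteria).
- GI-bleed window: 6 months before randomisation (Exclusion criteria), taken here as 180-183 days. The day count is an assumption.

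**Step 1. First dose to randomisation = part 1 + part 2**
- Shortest: 7 + 7 = 14 days.
- Longest: 10 + 13 = 23 days.
- With part 2 at its nominal 10 days: 7 + 10 = 17 to 10 + 10 = 20 days.

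**Step 2. Window guaranteed at first dose = stated window − interval from step 1**

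| Window | 14-day run-in | 23-day run-in | Share lost |
|---|---|---|---|
| Surgery, 30 days | 30 − 14 = 16 days | 30 − 23 = 7 days | 14/30 = 47% to 23/30 = 77% |
| GI bleed, 180 days | 180 − 14 = 166 days | 180 − 23 = 157 days | 14/180 = 8% to 23/180 = 13% |
| GI bleed, 183 days | 183 − 14 = 169 days | 183 − 23 = 160 days | 14/183 = 8% to 23/183 = 13% |

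At nominal part 2 length, the surgery window at first dose is 30 − 20 = 10 to 30 − 17 = 13 days. For GI bleed, 157/30 = 5.2 months and 169/30.5 = 5.5 months remain.

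**Step 3. A concrete case.** A patient 31 days past major surgery at randomisation is eligible. That patient took the first study dose 31 − 23 = 8 to 31 − 14 = 17 days after surgery.

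**Step 4. Is the gap closed elsewhere?** No other text ties either window to the first dose. Active bleeding, bleeding diathesis, low platelets and low haemoglobin are excluded separately, but none of these supplies a post-surgical interval.

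**The case against.** The strongest reply is that the order of procedures largely deals with this. Eligibility is verified before any study drug is given, when the randomisation date is still unknown. Counting back from the screening date is the simpler practice and closes the gap. For the gap to open, staff must see a patient operated on 8-17 days ago and clear that patient on a projected randomisation date. The lower end also needs both run-in parts to reach their maximum. Staff who want certainty must assume the 14-day minimum, which puts the first dose no earlier than day 17.

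Much of this stands. The 77% loss is a literal extreme. But staff who assume the 14-day minimum still leave only 16 of the 30 days, and the schedule permits the longer run-in. The written criterion points to a future date, and nothing tells staff to use the safer reading.

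It is also fair that participants already take antiplatelet therapy, so for some the run-in adds little or nothing, and that percentage of window lost does not measure bleeding risk. The documents give neither a rationale for 30 days nor a frequency of recent surgery. Finally, the randomisation date has a real use: it catches surgery or a GI bleed during the run-in. That is a reason to keep it, not to rely on it alone.

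**Conclusion.** The concern holds as a point to consider. The criterion is consistent with the design but protects for less time than its stated lengths suggest. The shortfall at first dose is notable for surgery (7-16 days guaranteed instead of 30; 10-13 days at nominal part 2 length) and small for GI bleed (8-13%).

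This rests on a literal reading of the criterion, the run-in durations as written, and 6 months taken as 180-183 days. The arithmetic is certain; the practical consequence is not, because it depends on how staff apply the rule and on how many candidates had recent surgery. The primary endpoint, sample size and analysis are unaffected.

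**What to change.** Require both windows at the first run-in dose and keep a check at randomisation. Possible wording: exclude patients with a GI bleed in the 6 months, or major surgery in the 30 days, before the first dose of run-in medication, or with either event between that dose and randomisation.

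The second half is needed because the active-bleeding exclusion would not catch a run-in GI bleed that has stopped, or surgery during the run-in. The investigators' window lengths are unchanged. For surgery before the run-in, the interval at randomisation would then be at least 30 + 14 = 44 to 30 + 23 = 53 days, depending on run-in length.

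The cost is a one-sentence amendment. Any candidate caught by the stricter rule would start the run-in at most 14-23 days later than the current wording allows. Nothing changes in the endpoint, sample size or analysis.
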